**f. Serious Adverse Event:**

An SAE is defined as an AE meeting one of the following conditions:

- Results in death during the period of protocol defined surveillance, except deaths that are the result of trauma or accident.
- Is life-threatening (defined as a subject at immediate risk of death at the time of the event).
- Requires inpatient hospitalization or prolongation of existing hospitalization during the period of protocol-defined surveillance.
- Results in a persistent or significant disability/incapacity.
- A congenital anomaly/birth defect.
- Any other important medical event that may not result in death, be life threatening, or require hospitalization, may be considered an SAE when, based upon appropriate medical judgment, the event may jeopardize the subject and may require medical or surgical intervention to prevent one of the outcomes listed above. Examples of such medical events include allergic bronchospasm requiring intensive treatment in an emergency room or at home, blood dyscrasias or convulsions that do not result in inpatient hospitalization, or the development of drug dependency or drug abuse.

The SAE should not be attributable to underlying disease for which the transplant was undertaken, or not attributable to GVHD, or not attributable to complications of immunosuppressive medications.

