## 7. Reporting Adverse Events:

The investigator is responsible for reporting:

- Any Grade 3 Adverse event that is not attributable to underlying disease for which the transplant was undertaken, **or** not attributable to GVHD, **or** not attributable to complications of immunosuppressive medications that are observed or reported through 7 days following vaccination (Day 0 through Day 7), regardless of their relationship to study product.
- Any other AE will not be reported unless it meets the SAE criteria (see Section 16.f).

Initial vaccine reactions will be assessed for at least 15 minutes after each vaccination. Subjects will be asked to record both solicited vaccine reactions and any unsolicited AEs on a memory aid for 7+ days after each vaccination (Day 0 through Day 7). Study personnel will attempt to contact the subjects by telephone and/or electronic communication at 1-3 days and 8-10 days after vaccination to review any AEs and SAEs. Adverse events and SAEs will be collected through 7 days following vaccination.

**Solicited systemic AEs** will be collected for 7+ days post each vaccination and will include the following: fevers, headache, fatigue/malaise, nausea, body ache/myalgia, general activity level, and vomiting. **Solicited injection site AEs** will include the following: pain, tenderness, redness/erythema, and swelling/induration at injection site.

**Reporting of Deviations:** All deviations will be reported to the Institutional Review Board (IRB) at the time of annual continuing review. Note: if the deviation affects patient safety and/or risk, the event will be reported immediately.

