**Visit 2: Days 28-42:**

- Solicited AEs/unsolicited AEs will be reviewed and recorded.
- Medical history changes

- Concomitant medications will be recorded.
- Inclusion/exclusion criteria will be checked- patients will be eligible to receive vaccine 2 if they received vaccine 1, regardless of GVHD status changes but the changes need to be documented.
- Targeted physical examination will be conducted including measurement of oral temperature (must be <100.4°F/38°C). If a physical exam is completed as a part of standard of care, another physical exam does not need to be completed.
- For females of childbearing potential a pregnancy test will be performed
- Approximately 30-60 mL of blood will be collected by venipuncture or from a central line prior to vaccination for HAI and MN assays to influenza virus antigens, phenotypic B, and T cell responses, B and T cell specific influenza responses, CBC d/p, quantitative CD4+/CD8+/CD19+ levels, and quantitative serum IgG and IgM concentrations.
- Study vaccine will be administered
- Study staff will observe the subjects closely for at least 15 minutes post-vaccination, with appropriate medical treatment readily available in case of rare anaphylactic reaction following the administration of vaccines.
- If IVIG/SCIG is given the same day, it must be given after the vaccination, and a second blood draw will be obtained post-IVIG/SCIG if administered on same calendar day.
- A memory aid form with reaction measurements, a measurement gauge, thermometer and instructions will be provided for the subject to record oral temperatures and any general or local reactions occurring during the vaccination day (day 0) and the next 7 days. Information from the memory aid form will be collected from the subject through telephone calls or emails in the week following vaccination. If memory aid data were not received by any of the methods mentioned, subjects may return it on the day of their next visit.
- The subject will be given contact information for study personnel. The subject will be educated about any potential reactions following vaccination. They will be instructed to contact study personnel for reactions that are Grade 3, as well as any other medical event that is concerning to subject.
- A nasal swab for PCR testing for influenza and other respiratory viruses will be obtained regardless of symptoms.

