**d. Relationship to study products/vaccines:** The investigator's assessment of the relationship of an AE to the study drug/vaccine is part of the documentation process, but it is not a factor in determining what is or is not reported in the study. If there is any doubt as to whether a clinical observation is an AE, the event should be reported. AEs must have their possible relationship to study vaccine assessed using the following terms: related or not related. In a clinical trial, the study product must always be suspect. To help assess, the following guidelines are used.

- **Related** – The event is temporally related to the administration of the study product and no other etiology explains the event.
- **Not Related** – The event is temporally independent of study product and/or the event appears to be explained by another etiology.

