**g. Reporting Procedures:**

Adverse events including local and systemic reactions not meeting the criteria for SAEs will be captured on the appropriate case report form (CRF). Information to be collected for unsolicited adverse events includes event description, date of onset, investigator assessment of severity, investigator assessment of relationship to study product, date of resolution of the event, seriousness, and outcome. The severity of non-serious AEs will be assessed by a licensed clinician (i.e., medical doctor, nurse, nurse practitioner, physician's assistant). The relationship of non-serious AEs will be assessed by a licensed clinician (i.e., medical doctor, nurse practitioner, physician assistant) listed on the Form FDA 1572. AEs occurring during the AE reporting period of the study will be documented appropriately regardless of relationship. AEs will be followed to adequate resolution or until considered stable.

Any medical condition that is present at screening will be considered a baseline condition and will not be reported as an AE. If the severity of any pre-existing medical condition increases during the study period, then it will be recorded as an AE.

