**h. Serious Adverse Event Detection and Reporting:**

SAEs as defined in Section 16.f will be:

- Notified to the Investigational New Drug (IND) Sponsor/Lead primary investigator (PI) ([name]) local site PI and/or Sub-Investigators and The Division of Microbiology and Infectious Diseases (DMID) Pharmacovigilance Group (PVG) within 24 hours of knowledge of the SAE.
- Assessed for severity and relationship by a licensed clinician listed on the FDA Form 1572 as the PI or a Sub-Investigator.
- Recorded on the appropriate SAE report form.
- Followed through resolution by a study physician.
- Reviewed by an Independent Safety Monitor (ISM), Data and Safety Monitoring Board (DSMB) (periodic review unless related), DMID, and IRB.
- SAEs related to the study vaccine that are unexpected, and fatal or life-threatening will be reported to the FDA no later than 7 calendar days after SAE awareness.
- SAEs related to the study vaccine that are unexpected and serious (not fatal or life-threatening) are to be reported to the FDA no later than 15 calendar days after SAE awareness.
- All other SAEs will be submitted with the FDA Annual Report in summary form.
- SAEs deemed related to the study vaccine and unexpected will be reported to Sanofi within 7-15 calendar days after SAE awareness.

SAEs occurring within 7 days of vaccination that are deemed related will also be reported to the local IRB within 1-2 calendar days as the team becomes aware of the SAE or per local IRB protocol/procedures.

Any AE that meets a protocol-defined serious criterion as defined in Section 16.f will be submitted immediately (within 24 hours of site awareness) on a SAE form to the DMID Pharmacovigilance Group, to the following address:

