groups will be estimated by calculating the posterior 95% credible interval of the difference in proportions. For continuous-valued events (e.g. size of swelling) uninformative priors will be used as described in (17.b); for discrete events, a flat beta parameter with scale=shape=1 will be used as uninformative priors. For each group and each event, solicited and unsolicited AEs will be descriptively summarized. Severities of solicited and unsolicited AEs will also be descriptively summarized for each group and each type of event. Descriptive statistics will include number experiencing event, mean and 95% posterior credible interval. Maximum size of redness and swelling may be descriptively summarized for each group and event; proportion of events lasting longer beyond Day 3 may also be descriptively summarized. Subjects with missing data will be excluded from analysis, but the sensitivity of the results to missingness will be formally analyzed by comparing posterior estimates under the range of possible outcomes for the missing individuals.

- d. Influenza-Like-Illness assessment:** The percentage of individuals in each group that test positive for influenza by PCR and the number of ILIs in each group during the influenza season will be compared.

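### Severe and serious events attributed to GVHD, underlying disease or immunosuppression are kept out of reporting by some sections and required by others, so the AE/SAE summary would omit them on site judgement

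*Combined protocol and SAP*

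**What the plan says.** Five parts of the protocol bear on whether a severe event blamed on the transplant enters the data.

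- **Grade 3 events (Sections 7 and 16.a).** The investigator reports "Any Grade 3 Adverse event that is not attributable to underlying disease for which the transplant was undertaken", or to GVHD, or to complications of immunosuppressive medication, within 7 days of vaccination. The same bullet adds that relationship to the study product does not matter. The next bullet closes the other route: "Any other AE will not be reported unless it meets the SAE criteria".
- **Serious events (Sections 16.f and 16.h).** After the usual seriousness criteria, 16.f states: "The SAE should not be attributable to underlying disease for which the transplant was undertaken, or not attributable to GVHD", with immunosuppressive complications as the third cause. Section 16.h opens with "SAEs as defined in Section 16.f will be" and then lists the recipients and reviewers: the IND sponsor, DMID, the independent safety monitor, the DSMB, the IRB and the FDA.
- **Relationship and documentation (Sections 16.d and 16.g).** On the relationship assessment, 16.d says "it is not a factor in determining what is or is not reported in the study". Section 16.g says "AEs occurring during the AE reporting period of the study will be documented appropriately regardless of relationship", and adds that a condition present at screening which becomes more severe is recorded as an AE.
- **GVHD status (Section 14, Visit 2).** Vaccine 2 is allowed "regardless of GVHD status changes but the changes need to be documented".
- **Analysis (Section 17.c).** The primary safety analysis is the proportion with at least one solicited AE. Beyond that, "solicited and unsolicited AEs will be descriptively summarized" for each group and event, with severity. No GVHD table is planned.

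**The concern.** Hypothesis 2 expects HD-TIV to have a safety profile similar to SD-QIV. The population is allogeneic transplant recipients, and those with stable GVHD may enrol. The protocol treats GVHD as important elsewhere: it governs eligibility, its steroid treatment enters the randomisation blocks, and its grade is collected.

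If cause is judged before an event is recorded, the reader of the AE/SAE tables cannot see how many severe or serious events were set aside, in which arm, or on what grounds. A tabulated attribution can be re-examined later; an event that was never entered cannot. Four sites working from contradictory sections, and from a sentence that can be read in opposite ways, may also record the same event differently.

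**Working it through.** The point rests on no figure in the plan, so the check is a comparison of sections, followed by a calculation of what the repaired tables could show.

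**1. Follow one event.** Take a subject with stable GVHD at screening who is hospitalised on day 4 after a dose, where the site puts the event down to GVHD.

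- Sections 7 and 16.a, as intended: not a reportable Grade 3 event, because of its cause.
- Section 7, second bullet: reportable only if it is an SAE.
- Section 16.f, as intended: not an SAE, because of its cause.
- Section 16.h: nothing to route, since it starts from the 16.f definition.
- Section 16.g: recorded as an AE, both as a worsened pre-existing condition and under the documentation rule.

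The same event is both excluded and required.

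**2. Section 16.d conflicts only indirectly.** Its rule concerns relationship to the vaccine. But its definition of an unrelated event includes one explained by another etiology. Attributing an event to GVHD is therefore in effect an unrelated judgement, and under 16.f that judgement decides reporting. Section 16.g is the direct contradiction.

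**3. The wording of the exclusion.** Let A, B and C mean that an event is attributed to underlying disease, GVHD or immunosuppression. There are 2³ = 8 combinations.

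- Literal reading, keep if (not A) or (not B) or (not C): only A, B and C together is excluded, 1 of 8.
- Evident intent, keep if (not A) and (not B) and (not C): every combination with at least one cause is excluded, 8 − 1 = 7 of 8.

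These count combinations, not patients. An event attributed to GVHD alone is kept under the first reading and dropped under the second.

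**4. Grades.** Section 7 does not report non-serious Grade 1–2 unsolicited events. Section 16.g captures non-serious AEs on the case report form with severity. Section 17.c summarises unsolicited AEs by severity. Which grades will be available is not settled.

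**5. Precision of a repaired table.** Inputs: 69 per arm (Section 17.a) and the beta(1,1) prior (Section 17.c). The documents give no GVHD or SAE rate, so the rates are assumed. With x events of n in each arm, each posterior is Beta(x+1, n−x+1), with variance (x+1)(n−x+1)/[(n+2)²(n+3)]. For n = 69 the denominator is 71² × 72 = 362,952. The approximate 95% half-width for the difference is 1.96 × √(2 × variance).

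- About 5% (x = 3): variance 4 × 67/362,952 = 0.00074; half-width 0.075.
- About 10% (x = 7): 8 × 63/362,952 = 0.00139; half-width 0.103.
- About 20% (x = 14): 15 × 56/362,952 = 0.00231; half-width 0.133.
- About 50% (x = 34): 35 × 36/362,952 = 0.00347; half-width 0.163.

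Simulation from the posteriors gives the same limits to within 0.2 points.

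As a test, assume two-sided 5% and the normal two-proportion formula, power = Φ{[d√n − 1.96√(2p̄(1−p̄))] / √(p₁(1−p₁)+p₂(1−p₂))}. For 10% against 20%: [0.1 × 8.307 − 1.96 × √0.255]/√0.25 = (0.831 − 0.990)/0.5 = −0.32, so power is about 38%. The same formula gives about 20%, 73% and 95% for a doubling from 5%, 20% and 30%.

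**The case against.** The strongest reply is that the exclusion is a deliberate and separate question from relatedness. Sections 7 and 16.a state both in one bullet, and background events are frequent after transplant. Aim 2 and the safety objectives concern solicited events, which subjects record on the memory aid. This stands in part: the solicited-event analysis is largely untouched, and a filter for expedited reporting is defensible. It does not remove the conflict with 16.g or the ambiguity of 16.f.

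A reader might infer three stronger conclusions that the documents do not support.

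- *The trial cannot show a GVHD difference.* GVHD changes after dose 1 must be documented at Visit 2, and concomitant medication is scheduled through Visit 3. A comparison after dose 1 is possible; it is only not planned. The 7-day window and the sample size would also limit it without any exclusion.
- *The DSMB sees only filtered events.* Section 16.i lets its reports include medical history, concomitant medication, physical assessments and laboratory values, and lets it request more.
- *The arm comparison is biased.* Randomisation is balanced within site and study staff are blinded, so differences in applying the filter should fall on both arms alike. Differential filtering is not shown. What remains is lost information.

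It is also arguable that Section 7 distinguishes reporting from capture, in which case low-grade unsolicited events are available for 17.c. The text does not settle this, so it should be clarified rather than the summary simply cut.

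**Conclusion.** The concern holds as an inconsistency with a real consequence. On their evident reading, Sections 7, 16.a and 16.f keep Grade 3 and serious events attributed to GVHD, underlying disease or immunosuppression out of reporting; 16.g directly requires the opposite, and 16.d does so indirectly. Following the exclusions would leave GVHD-attributed events out of the planned AE/SAE summary on each site's judgement.

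The number of events affected cannot be stated, because the documents give no rate. What a repaired table could show is limited: about ±8 to ±16 percentage points for assumed rates of 5% to 50% with all 69 per arm observed, and wider with dropout. The benefit is completeness and an honest interval, not a test of GVHD risk. The conclusion assumes that sites apply the evident intent of 16.f rather than its literal logic.

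**What to change.** 1. Reconcile Sections 7, 16.a and 16.f with 16.d and 16.g. Every Grade 3 AE and every event meeting a seriousness criterion within the existing 7-day window should be recorded, with attribution to underlying disease, GVHD or immunosuppression as a data field. An attribution filter may stay for expedited reporting, worded so that it has one meaning.
2. State whether the similar cause-based exclusion in the halting rules (Section 16.j) is intended. No change to those rules is proposed here.
3. In Section 17.c, add two tables by arm, with the between-arm difference and its 95% credible interval under the beta(1,1) prior: all-cause SAEs in the 7-day window, and the GVHD status changes documented at Visit 2. Label both as estimates.
4. State which grades of unsolicited AE are collected, and align the 17.c severity summary with that.

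Extending the GVHD comparison to Visit 3 is optional: that visit lists no GVHD entry, so it needs an added data field.

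The cost is protocol wording, two short tables, and somewhat more background events to record and review. No dose or visit changes. The current version is dated August 2019, after the two seasons set for recruiting new subjects, so events already left out could be recovered only from source records. The Visit 2 table avoids this if those changes were documented in the earlier seasons as the current text requires.

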**g. Reporting Procedures:**

Adverse events including local and systemic reactions not meeting the criteria for SAEs will be captured on the appropriate case report form (CRF). Information to be collected for unsolicited adverse events includes event description, date of onset, investigator assessment of severity, investigator assessment of relationship to study product, date of resolution of the event, seriousness, and outcome. The severity of non-serious AEs will be assessed by a licensed clinician (i.e., medical doctor, nurse, nurse practitioner, physician's assistant). The relationship of non-serious AEs will be assessed by a licensed clinician (i.e., medical doctor, nurse practitioner, physician assistant) listed on the Form FDA 1572. AEs occurring during the AE reporting period of the study will be documented appropriately regardless of relationship. AEs will be followed to adequate resolution or until considered stable.

Any medical condition that is present at screening will be considered a baseline condition and will not be reported as an AE. If the severity of any pre-existing medical condition increases during the study period, then it will be recorded as an AE.

**h. Serious Adverse Event Detection and Reporting:**

SAEs as defined in Section 16.f will be:

- Notified to the Investigational New Drug (IND) Sponsor/Lead primary investigator (PI) ([name]) local site PI and/or Sub-Investigators and The Division of Microbiology and Infectious Diseases (DMID) Pharmacovigilance Group (PVG) within 24 hours of knowledge of the SAE.
- Assessed for severity and relationship by a licensed clinician listed on the FDA Form 1572 as the PI or a Sub-Investigator.
- Recorded on the appropriate SAE report form.
- Followed through resolution by a study physician.
- Reviewed by an Independent Safety Monitor (ISM), Data and Safety Monitoring Board (DSMB) (periodic review unless related), DMID, and IRB.
- SAEs related to the study vaccine that are unexpected, and fatal or life-threatening will be reported to the FDA no later than 7 calendar days after SAE awareness.
- SAEs related to the study vaccine that are unexpected and serious (not fatal or life-threatening) are to be reported to the FDA no later than 15 calendar days after SAE awareness.
- All other SAEs will be submitted with the FDA Annual Report in summary form.
- SAEs deemed related to the study vaccine and unexpected will be reported to Sanofi within 7-15 calendar days after SAE awareness.

SAEs occurring within 7 days of vaccination that are deemed related will also be reported to the local IRB within 1-2 calendar days as the team becomes aware of the SAE or per local IRB protocol/procedures.

Any AE that meets a protocol-defined serious criterion as defined in Section 16.f will be submitted immediately (within 24 hours of site awareness) on a SAE form to the DMID Pharmacovigilance Group, to the following address:

#### **i. Independent Safety Monitor (ISM) and the Data Safety Monitoring Board (DSMB):**

An Independent Safety Monitor (ISM) is a physician at the enrollment site with relevant expertise whose primary responsibility is to provide independent medical assessment in a timely fashion at each site. Each site will have an ISM and back-up ISM. Participation is for the duration of the study. All ISMs and future ISMs will be assessed for Conflict of Interest (COI) according to the National Institute of Allergy and Infectious Diseases (NIAID) policy, and only those ISMs who have no COI will be allowed to serve.

The ISM should be able to readily access participant records in real time, have the privileges to examine the subject, and provide an independent medical assessment and recommendation to the IND sponsor and DMID. The primary focus of the ISM is to independently review all SAEs with follow-up through resolution and thoroughly investigate those events considered unexpected. Clinical and laboratory data, clinical records, and other study-related records should be made available for ISM review. The ISM may be a faculty member at the clinical site but will not be under the direct supervision of the PI. It is the responsibility of the PI to ensure that the ISM is apprised of all new safety information relevant to the study product and the study.

Safety oversight will be conducted by a DSMB that is an independent group with expertise to interpret data from this study and will monitor subject safety and advise DMID and the IND sponsor. The DSMB members will be separate and independent of study personnel participating in this study and should not have scientific, financial, or other conflict of interest related to this study. All DSMB members and future DSMB members will be assessed for COI according to the NIAID policy, and only those DSMB members who have no COI will be allowed to serve. The DSMB will consist of a minimum of 3 members. A simple majority will be considered a quorum for meeting purposes.

The DSMB operations will be in compliance with the NIAID policy and will be so described in the charter which will be shared with DMID. The DSMB will operate under the rules of a DMID-approved charter that will be written at the organizational meeting of the DSMB and defines the data elements to be assessed and the

procedures for data reviews. At this time, each data element that the DSMB needs to assess will be clearly defined. Procedures for DSMB reviews/meetings will be defined in the charter. The DSMB will review applicable data to include, but not limited to, overall study progress and participant, clinical, safety, and reactogenicity data. Reports may include enrollment and demographic information, medical history, concomitant medications, physical assessments, clinical laboratory values, dosing compliance, and solicited and unsolicited AE/SAEs. Additional data may be requested by the DSMB, and interim statistical reports may be generated as deemed necessary and appropriate by the IND sponsor and DMID. The DSMB may receive data in aggregate and presented by treatment arm. The DSMB may also be provided with expected and observed rates of the expected AEs in an un-blinded fashion, and may request the treatment assignment be un-blinded for an individual subject if required for safety assessment. The DSMB will review grouped and un-blinded data in the closed session only. The DSMB will meet and review this data at scheduled time points or ad hoc as needed during this study as defined in the DSMB charter. As an outcome of each review/meeting, the DSMB will make a recommendation to the IND sponsor and DMID as to the advisability of proceeding with study vaccinations (as applicable), and to continue, modify, or terminate this trial.

DMID or the DSMB chair may convene the DSMB on an ad hoc basis according to protocol criteria or if there are immediate concerns regarding observations during the course of this trial. The IND sponsor and/or DMID Medical Monitor is empowered to stop enrollment and study vaccinations if adverse events that meet the halting criteria are reported. The IND sponsor, DMID Medical Monitor and the ISM will be responsible for reviewing SAEs in real time. The DSMB will review SAEs on a regular basis and ad hoc during this study.

The DSMB will review study progress and participant, clinical, safety, and reactogenicity data at the following times:

- Data review for safety and reactogenicity at specified times during the course of this trial – every 6 months, starting after the first patient is enrolled until the end of the study.
- Final review – 6 to 8 months after clinical database lock to review the cumulative un-blinded safety, and reactogenicity data for this study. The data will be provided in a standard summary format. The DSMB may be asked to provide recommendations in response to questions posed by the IND sponsor and DMID.
- Ad hoc when a halting rule is met, for immediate concerns regarding observations during this study, or as needed – for a specific safety concern, such as SAE deemed related to the study vaccine.

The DMID Medical Monitor will:

- receive access to the open session materials;
- be invited to the open session of the DSMB discussion;
- be informed promptly on the DSMB recommendations; and
- be copied on the official DSMB recommendations.

